Appendix B

Colonoscopy; n (%)	409 (3.7%)	230 (3.6%)	0.01	966 (4.2%)	347 (3.7%)	0.03	1,620 (4.9%)	772 (4.8%)	0.00	2995 (4.5%)	1349 (4.2%)	0.01
Fecal occult blood (FOB) test; n (%)	340 (3.1%)	183 (2.8%)	0.02	886 (3.8%)	308 (3.3%)	0.03	937 (2.8%)	436 (2.7%)	0.01	2163 (3.2%)	927 (2.9%)	0.02
Flu vaccine; n (%)	1,631 (14.9%)	967 (15.0%)	0.00	2,149 (9.3%)	1,007 (10.7%)	-0.05	10,466 (31.8%)	5,207 (32.1%)	-0.01	14246 (21.3%)	7181 (22.4%)	-0.03
Mammogram; n (%)	1,237 (11.3%)	704 (10.9%)	0.01	2,232 (9.7%)	938 (10.0%)	-0.01	4,385 (13.3%)	2,227 (13.7%)	-0.01	7854 (11.7%)	3869 (12.1%)	-0.01
Pap smear; n (%)	651 (6.0%)	384 (6.0%)	0.00	1,873 (8.1%)	773 (8.2%)	0.00	963 (2.9%)	514 (3.2%)	-0.02	3487 (5.2%)	1671 (5.2%)	0.00
Pneumonia vaccine; n (%)	1,134 (10.4%)	1,158 (18.0%)	-0.22	988 (4.3%)	793 (8.4%)	-0.17	6,053 (18.4%)	4,358 (26.9%)	-0.20	8175 (12.2%)	6309 (19.7%)	-0.21
PSA test or Prostate exam for DRE; n (%)	1,083 (9.9%)	690 (10.7%)	-0.03	1,944 (8.4%)	818 (8.7%)	-0.01	3,705 (11.3%)	2,058 (12.7%)	-0.04	6732 (10.1%)	3566 (11.1%)	-0.03
Bone mineral density; n (%)	317 (2.9%)	200 (3.1%)	-0.01	396 (1.7%)	143 (1.5%)	0.02	1,608 (4.9%)	809 (5.0%)	0.00	2321 (3.5%)	1152 (3.6%)	-0.01
Use of CNS stimulants; n (%)	85 (0.8%)	70 (1.1%)	-0.03	335 (1.5%)	129 (1.4%)	0.01	133 (0.4%)	72 (0.4%)	0.00	553 (0.8%)	271 (0.8%)	0.00
Use of estrogens, progestins, androgens; n (%)	1,084 (9.9%)	683 (10.6%)	-0.02	3,192 (13.9%)	1,414 (15.0%)	-0.03	1,380 (4.2%)	655 (4.0%)	0.01	5656 (8.5%)	2752 (8.6%)	0.00
Use of Angiogenesis inhibitors; n (%)	** (0.1%)	** (0.0%)	0.04	18 (0.1%)	** (0.0%)	0.04	21 (0.1%)	** (0.0%)	0.04	#VALUE!	#VALUE!	#VALUE!
Use of Oral Immunosuppressants; n (%)	24 (0.2%)	** (0.2%)	0.00	75 (0.3%)	18 (0.2%)	0.02	20 (0.1%)	** (0.1%)	0.00	119 (0.2%)	#VALUE!	#VALUE!
Use of fondaparinux or Bivalirudin; n (%)	137 (1.3%)	** (0.1%)	0.14	430 (1.9%)	15 (0.2%)	0.17	250 (0.8%)	** (0.1%)	0.10	817 (1.2%)	#VALUE!	#VALUE!
Use of other direct thrombin inhibitors (lepirudin, desirudin, argatroban); n (%)	0 (0.0%)	0 (0.0%)	#DIV/0!	0 (0.0%)	0 (0.0%)	#DIV/0!	0 (0.0%)	0 (0.0%)	#DIV/0!	0 (0.0%)	0 (0.0%)	#DIV/0!
Use of Ticagrelor ON CED; n (%)	** (0.0%)	** (0.1%)	-0.04	** (0.0%)	** (0.0%)	#DIV/0!	0 (0.0%)	** (0.0%)	#DIV/0!	#VALUE!	#VALUE!	#VALUE!
Use of Ticagrelor; n (%)	** (0.0%)	** (0.1%)	-0.04	** (0.0%)	** (0.1%)	-0.04	22 (0.1%)	19 (0.1%)	0.00	#VALUE!	#VALUE!	#VALUE!
Number of D-dimer tests												
...mean (sd)	0.12 (0.36)	0.16 (0.42)	-0.10	0.13 (0.38)	0.14 (0.39)	-0.03	0.14 (0.36)	0.17 (0.40)	-0.08	0.13 (0.37)	0.16 (0.40)	0.00
Number of CRP, high-sensitivity CRP tests												
...mean (sd)	0.10 (0.47)	0.12 (0.53)	-0.04	0.09 (0.48)	0.09 (0.45)	0.00	0.13 (0.55)	0.14 (0.57)	-0.02	0.11 (0.51)	0.12 (0.53)	0.00
Number of PT or aPTT tests												
...mean (sd)	0.66 (1.77)	0.58 (1.39)	0.05	0.58 (1.48)	0.47 (1.22)	0.08	0.38 (0.91)	0.35 (0.74)	0.04	0.49 (1.29)	0.43 (1.05)	0.00
Number of Bleeding time tests												
...mean (sd)	0.00 (0.02)	0.00 (0.01)	0.00	0.00 (0.02)	0.00 (0.01)	0.00	0.00 (0.03)	0.00 (0.02)	0.00	0.00 (0.03)	0.00 (0.02)	0.00
HAS-BLED Score (ICD-9 and ICD-10), 180 days												
...mean (sd)	2.68 (1.05)	2.55 (1.03)	0.12	2.28 (0.98)	2.21 (0.95)	0.07	3.43 (0.79)	3.39 (0.80)	0.05	2.91 (0.90)	2.88 (0.90)	0.00
N of Generic name drugs												
...mean (sd)	15.36 (13.41)	13.47 (14.05)	0.14	13.18 (11.45)	11.66 (11.95)	0.13	18.30 (13.64)	16.35 (14.30)	0.14	16.06 (12.89)	14.40 (13.60)	0.00
N of Brand name drugs												
...mean (sd)	2.98 (4.53)	3.58 (3.90)	-0.14	3.30 (4.45)	3.75 (3.79)	-0.11	3.22 (4.77)	3.92 (4.27)	-0.15	3.21 (4.62)	3.80 (4.06)	0.00
Use of clopidogrel; n (%)	259 (2.4%)	122 (1.9%)	0.03	499 (2.2%)	145 (1.5%)	0.05	1,670 (5.1%)	716 (4.4%)	0.03	2428 (3.6%)	983 (3.1%)	0.03
Systemic embolism; n (%)	221 (2.0%)	112 (1.7%)	0.02	404 (1.8%)	141 (1.5%)	0.02	462 (1.4%)	200 (1.2%)	0.02	1087 (1.6%)	453 (1.4%)	0.02
DVT; n (%)	5,150 (47.1%)	3,078 (47.7%)	-0.01	10,806 (46.9%)	4,578 (48.7%)	-0.04	14,349 (43.6%)	6,958 (42.9%)	0.01	30305 (45.3%)	14614 (45.6%)	-0.01
Post-thrombotic syndrome; n (%)	** (0.1%)	** (0.1%)	#DIV/0!	14 (0.1%)	** (0.1%)	#DIV/0!	21 (0.1%)	12 (0.1%)	#DIV/0!	14 (0.1%)	** (0.1%)	0.00
PE; n (%)	10,931 (100.0%)	6,448 (100.0%)	#DIV/0!	23,030 (100.0%)	9,398 (99.9%)	0.04	32,865 (99.9%)	16,217 (100.0%)	-0.04	66826 (99.9%)	32063 (100.0%)	-0.04
Coagulation defects; n (%)	285 (2.6%)	123 (1.9%)	#DIV/0!	654 (2.8%)	211 (2.2%)	#DIV/0!	579 (1.8%)	213 (1.3%)	#DIV/0!	654 (2.8%)	211 (2.2%)	0.04
Diabetes: 1 inpatient or 2 outpatient claims within 183 days; n (%)	2,243 (20.5%)	1,185 (18.4%)	0.05	3,626 (15.7%)	1,408 (15.0%)	0.02	8,179 (24.9%)	3,686 (22.7%)	0.05	14048 (21.0%)	6279 (19.6%)	0.03
Intracranial or retroperitoneal hemorrhage: 1 inpatient or 2 outpatient claims within 183 days; n (%)												
** (0.0%)	** (0.0%)	#DIV/0!	** (0.0%)	** (0.0%)	#DIV/0!	15 (0.0%)	** (0.0%)	#DIV/0!	#VALUE!	#VALUE!	#VALUE!	#VALUE!
Peptic Ulcer Disease; n (%)	2,932 (26.8%)	1,734 (26.9%)	0.00	4,029 (17.5%)	1,736 (18.5%)	-0.03	11,261 (34.2%)	5,399 (33.3%)	0.02	18222 (27.2%)	8869 (27.6%)	-0.01
Major Surgery; n (%)	739 (6.8%)	491 (7.6%)	#DIV/0!	1,391 (6.0%)	507 (5.4%)	#DIV/0!	2,747 (8.4%)	1,625 (10.0%)	#DIV/0!	1,391 (6.0%)	507 (5.4%)	0.03
Upper GI bleed; n (%)	0 (0.0%)	0 (0.0%)	#DIV/0!	0 (0.0%)	0 (0.0%)	#DIV/0!	0 (0.0%)	0 (0.0%)	#DIV/0!	0 (0.0%)	0 (0.0%)	#DIV/0!
Lower /unspecified GI bleed; n (%)	0 (0.0%)	0 (0.0%)	#DIV/0!	0 (0.0%)	0 (0.0%)	#DIV/0!	0 (0.0%)	0 (0.0%)	#DIV/0!	0 (0.0%)	0 (0.0%)	#DIV/0!
Urogenital bleed; n (%)	73 (0.7%)	49 (0.8%)	-0.01	171 (0.7%)	81 (0.9%)	-0.02	** (0.0%)	** (0.0%)	#DIV/0!	#VALUE!	#VALUE!	#VALUE!
Other bleeds; n (%)	504 (4.6%)	232 (3.6%)	0.05	819 (3.6%)	301 (3.2%)	0.02	1,521 (4.6%)	607 (3.7%)	0.05	2844 (4.3%)	1140 (3.6%)	0.04
Prior cancer; n (%)	1,356 (12.4%)	1,060 (16.4%)	-0.11	1,964 (8.5%)	1,011 (10.7%)	-0.07	5,398 (16.4%)	3,537 (21.8%)	-0.14	8718 (13.0%)	5608 (17.5%)	-0.13
Antibiotics; n (%)	5,272 (48.2%)	3,095 (48.0%)	#DIV/0!	11,518 (50.0%)	4,633 (49.3%)	#DIV/0!	17,994 (54.7%)	8,891 (54.8%)	#DIV/0!	11,518 (50.0%)	4,633 (49.3%)	0.01
Aspirin; n (%)	63 (0.6%)	71 (1.1%)	-0.05	254 (1.1%)	137 (1.5%)	-0.04	158 (0.5%)	46 (0.3%)	0.03	475 (0.7%)	254 (0.8%)	-0.01
Aspirin/dipyridamole; n (%)	** (0.1%)	** (0.1%)	0.00	36 (0.2%)	** (0.1%)	0.03	109 (0.3%)	33 (0.2%)	0.02	#VALUE!	#VALUE!	#VALUE!
Other antiplatelet agents; n (%)	22 (0.2%)	13 (0.2%)	0.00	36 (0.2%)	** (0.1%)	0.03	139 (0.4%)	57 (0.4%)	0.00	197 (0.3%)	#VALUE!	#VALUE!
PGP inhibitors; n (%)	2,367 (21.6%)	1,341 (20.8%)	0.02	5,284 (22.9%)	1,997 (21.2%)	0.04	8,671 (26.4%)	4,164 (25.7%)	0.02	16322 (24.4%)	7502 (23.4%)	0.02
Other gastroprotective agents; n (%)	128 (1.2%)	85 (1.3%)	-0.01	287 (1.2%)	101 (1.1%)	0.01	581 (1.8%)	248 (1.5%)	0.02	996 (1.5%)	434 (1.4%)	0.01
Number of lipid tests ordered												
...mean (sd)	0.46 (0.71)	0.45 (0.88)	0.01	0.34 (0.71)	0.36 (0.78)	-0.03	0.56 (0.76)	0.58 (0.82)	-0.03	0.47 (0.74)	0.49 (0.82)	0.00
Proton pump inhibitor; n (%)	2,563 (23.4%)	1,362 (21.1%)	0.06	5,093 (22.1%)	1,943 (20.7%)	0.03	10,854 (33.0%)	4,940 (30.5%)	0.05	18510 (27.7%)	8245 (25.7%)	0.05
H2 receptor antagonist; n (%)	385 (3.5%)	201 (3.1%)	0.02	774 (3.4%)	305 (3.2%)	0.01	2,080 (6.3%)	891 (5.5%)	0.03	3239 (4.8%)	1397 (4.4%)	0.02
Vitamin K therapy; n (%)	** (0.0%)	0 (0.0%)	#DIV/0!	24 (0.1%)	0 (0.0%)	0.04	** (0.0%)	0 (0.0%)	#DIV/0!	#VALUE!	0 (0.0%)	#VALUE!
Number of INR (prothrombin) tests ordered												
...mean (sd)	0.45 (1.24)	0.31 (0.75)	0.14	0.43 (1.02)	0.31 (0.74)	0.13	0.35 (0.77)	0.31 (0.63)	0.06	0.39 (0.95)	0.31 (0.69)	0.00
Treating prescriber - Cardiologist; n (%)	6,854 (62.7%)	4,359 (67.6%)	-0.10	12,270 (53.3%)	5,766 (61.3%)	-0.16	21,746 (66.1%)	10,824 (67.7%)	-0.01	40870 (61.1%)	20949 (65.3%)	-0.09
Treating prescriber - Primary Care Physician; n (%)	9,965 (91.1%)	5,708 (88.5%)	0.09	9,641 (41.8%)	4,170 (44.3%)	-0.05	14,127 (42.9%)	6,722 (41.4%)	0.03	33733 (50.4%)	16600 (51.8%)	-0.03
Treating prescriber - Other; n (%)	10,881 (99.5%)	6,428 (99.7%)	-0.03	21,748 (94.4%)	8,758 (93.1%)	0.05	32,848 (99.9%)	16,207 (99.6%)	0.00	65477 (97.9%)	31393 (97.9%)	0.00
Alpha blockers; n (%)	747 (6.8%)	400 (6.2%)	0.02	1,170 (5.1%)	438 (4.7%)	0.02	3,271 (9.9%)	1,719 (10.6%)	-0.02	5188 (7.8%)	2557 (8.0%)	-0.01
CHA2DS2 VASc score, 180 days, V												
...mean (sd)	3.62 (1.72)	2.28 (1.64)	0.80	3.42 (1.47)	2.40 (1.69)	0.64	4.52 (1.74)	3.51 (1.84)	0.56	3.99 (1.65)	2.94 (1.76)	0.01
Use of Prasugrel; n (%)	** (0.1%)	** (0.2%)	-0.03	30 (0.1%)	** (0.1%)	0.00	** (0.0%)	** (0.0%)	#DIV/0!	#VALUE!	#VALUE!	#VALUE!
Use of Loop Diuretics+other diuretics+other hypertension drugs; n (%)	1,387 (12.7%)	633 (9.8%)	0.09	2,381 (10.3%)	795 (8.5%)	0.06	6,233 (18.9%)	2,624 (16.2%)	0.07	10001 (15.0%)	4052 (12.6%)	0.07
Commercial vs Medicare Advantage- Business Type												
Code - CORRECT ONE - OPTUM												
...Commercial; n (%)	5,252 (48.0%)	3352 (52.0%)	-0.08	5,642 (24.5%)	1822 (19.4%)	0.12	-	-	#VALUE!	10,894 (32.1%)	5174 (32.6%)	-0.01
...Medicare Advantage; n (%)	5,684 (52.0%)	3096 (48.0%)	0.08	17,398 (75.5%)	7583 (80.6%)	-0.12	-	-	#VALUE!	23,082 (67.9%)	10679 (67.4%)	0.01

Appendix B

Commercial vs Medicare Advantage- Business Type Code											
...COM = COMMERCIAL; n (%)	5,252 (48.0%)	3,352 (52.0%)	-0.08	-	-	-	-	#VALUE!	5,252 (48.0%)	3,352 (52.0%)	-0.08
...MCR = MEDICARE; n (%)	5,684 (52.0%)	3,096 (48.0%)	0.08	-	-	-	-	#VALUE!	5,684 (52.0%)	3,096 (48.0%)	0.08
...MCD = MEDICAL; n (%)	0 (0.0%)	0 (0.0%)	#DIV/0!	-	-	-	-	#VALUE!	0 (0.0%)	0 (0.0%)	#DIV/0!
...NONE = NO BUSINESS LINE CODE (added in 2015); n (%)	0 (0.0%)	0 (0.0%)	#DIV/0!	-	-	-	-	#VALUE!	0 (0.0%)	0 (0.0%)	#DIV/0!
...UNK = UNKNOWN (added in 2015); n (%)	0 (0.0%)	0 (0.0%)	#DIV/0!	-	-	-	-	#VALUE!	0 (0.0%)	0 (0.0%)	#DIV/0!
Commercial vs Medicare Advantage- Data Type											
...1 - Fee For Service; n (%)	-	-	15,188 (65.9%)	6,798 (72.3%)	-0.14	-	-	15,188 (65.9%)	6,798 (72.3%)	-0.14	
...2 - Encounter; n (%)	-	-	2,210 (9.6%)	785 (8.3%)	0.05	-	-	2,210 (9.6%)	785 (8.3%)	0.05	
...3 - Medicare; n (%)	-	-	4,938 (21.4%)	1,622 (17.2%)	0.11	-	-	4,938 (21.4%)	1,622 (17.2%)	0.11	
...4 - Medicare Encounter; n (%)	-	-	704 (3.1%)	200 (2.1%)	0.06	-	-	704 (3.1%)	200 (2.1%)	0.06	
Metropolitan Statistical Area- Urban (any MSA) vs Rural (non-MSA)											
...Urban; n (%)	-	-	18,451 (80.1%)	6,998 (74.4%)	0.14	-	-	18,451 (80.1%)	6,998 (74.4%)	0.14	
...Rural; n (%)	-	-	290 (1.3%)	433 (4.6%)	-0.20	-	-	290 (1.3%)	433 (4.6%)	-0.20	
...Unknown/Missing; n (%)	-	-	4,299 (18.7%)	1,974 (21.0%)	-0.06	-	-	4,299 (18.7%)	1,974 (21.0%)	-0.06	

Due to CMS cell suppression policy, all values less than 11 are denoted with **

Appendix B

Appendix B

Liver disease; n (%)	0 (0.0%)	0 (0.0%)	#DIV/0!	0 (0.0%)	0 (0.0%)	#DIV/0!	0 (0.0%)	0 (0.0%)	0 (0.0%)	0 (0.0%)	#DIV/0!
Osteoarthritis; n (%)	665 (30.9%)	642 (29.8%)	0.02	1,107 (19.5%)	1,110 (19.6%)	0.00	3,006 (37.3%)	2,998 (37.2%)	4778 (30.1%)	4750 (29.9%)	0.00
Other arthritis, arthropathies and musculoskeletal pain; n (%)	1,448 (67.3%)	1,425 (66.2%)	0.02	3,489 (61.5%)	3,441 (60.6%)	0.02	4,956 (61.5%)	4,958 (61.5%)	9893 (62.2%)	9824 (61.8%)	0.01
Dorsopathies; n (%)	797 (37.0%)	772 (35.5%)	0.02	1,632 (28.8%)	1,652 (29.1%)	-0.01	2,750 (34.1%)	2,772 (34.4%)	5179 (32.6%)	5196 (32.7%)	0.00
Fractures; n (%)	230 (10.7%)	225 (10.5%)	0.01	430 (7.6%)	402 (7.1%)	0.02	838 (10.4%)	816 (10.1%)	1498 (9.4%)	1443 (9.1%)	0.01
Falls v2; n (%)	186 (8.6%)	186 (8.6%)	0.00	166 (2.9%)	152 (2.7%)	0.01	313 (3.9%)	308 (3.8%)	665 (4.2%)	646 (4.1%)	0.01
Osteoporosis; n (%)	137 (6.4%)	178 (8.3%)	-0.07	153 (2.7%)	165 (2.9%)	-0.01	1,050 (13.0%)	1,096 (13.6%)	1,340 (8.4%)	1,439 (9.1%)	-0.02
Depression; n (%)	428 (19.9%)	441 (20.5%)	-0.01	810 (14.3%)	802 (14.1%)	0.01	1,481 (18.4%)	1,528 (18.9%)	2719 (17.1%)	2771 (17.4%)	-0.01
Anxiety; n (%)	409 (19.0%)	425 (19.7%)	-0.02	797 (14.0%)	791 (13.9%)	0.00	1,388 (17.2%)	1,389 (17.2%)	2594 (16.3%)	2605 (16.4%)	0.00
Sleep_Disorder; n (%)	245 (11.4%)	259 (12.0%)	-0.02	651 (11.5%)	697 (12.3%)	-0.02	827 (10.3%)	851 (10.6%)	1,723 (10.8%)	1,807 (11.4%)	-0.02
Dementia; n (%)	160 (7.4%)	171 (7.9%)	-0.02	134 (2.4%)	135 (2.4%)	0.00	842 (10.4%)	913 (11.3%)	1,136 (7.1%)	1,219 (7.7%)	-0.02
Delirium; n (%)	74 (3.4%)	87 (4.0%)	-0.03	104 (1.8%)	92 (1.6%)	0.02	306 (3.8%)	299 (3.7%)	484 (3.0%)	478 (3.0%)	0.00
Psychosis; n (%)	59 (2.7%)	66 (3.1%)	-0.02	65 (1.1%)	64 (1.1%)	0.00	219 (2.7%)	224 (2.8%)	343 (2.2%)	354 (2.2%)	0.00
Obesity; n (%)	704 (32.7%)	715 (33.2%)	-0.01	1,534 (27.0%)	1,531 (27.0%)	0.00	1,869 (23.2%)	1,896 (23.5%)	4,107 (25.8%)	4,142 (26.1%)	-0.01
Overweight; n (%)	111 (5.2%)	99 (4.6%)	0.03	156 (2.7%)	136 (2.4%)	0.02	369 (4.6%)	368 (4.6%)	636 (4.0%)	603 (3.8%)	0.01
Smoking; n (%)	690 (32.0%)	677 (31.4%)	0.01	934 (16.5%)	920 (16.2%)	0.01	3,048 (37.8%)	2,933 (36.4%)	4,672 (29.4%)	4,530 (28.5%)	0.02
Alcohol abuse or dependence; n (%)	62 (2.9%)	57 (2.6%)	0.02	129 (2.3%)	111 (2.0%)	0.02	106 (1.3%)	91 (1.1%)	297 (1.9%)	259 (1.6%)	0.02
Drug abuse or dependence; n (%)	78 (3.6%)	79 (3.7%)	-0.01	110 (1.9%)	111 (2.0%)	-0.01	90 (1.1%)	80 (1.0%)	278 (1.7%)	270 (1.7%)	0.00
COPD; n (%)	382 (17.7%)	428 (19.9%)	-0.06	582 (10.3%)	567 (10.0%)	0.01	1,887 (23.4%)	1,932 (24.0%)	2,851 (17.9%)	2,927 (18.4%)	-0.01
Asthma; n (%)	276 (12.8%)	297 (13.8%)	-0.03	628 (11.1%)	632 (11.1%)	0.00	900 (11.2%)	931 (11.5%)	1,804 (11.4%)	1,860 (11.7%)	-0.01
Obstructive sleep apnea; n (%)	309 (14.4%)	310 (14.4%)	0.00	689 (12.1%)	706 (12.4%)	-0.01	825 (10.2%)	824 (10.2%)	1,823 (11.5%)	1,840 (11.6%)	0.00
Pneumonia; n (%)	378 (17.6%)	411 (19.1%)	-0.04	856 (15.1%)	841 (14.8%)	0.01	1,435 (17.8%)	1,421 (17.6%)	2,669 (16.8%)	2,673 (16.8%)	0.00
Other Medications											
Use of ACE inhibitors; n (%)	487 (22.6%)	520 (24.2%)	-0.04	1,094 (19.3%)	1,090 (19.2%)	0.00	2,376 (29.5%)	2,459 (30.5%)	3957 (24.9%)	4069 (25.6%)	-0.02
Use of ARBs; n (%)	323 (15.0%)	332 (15.4%)	-0.01	691 (12.2%)	745 (13.1%)	-0.03	1,583 (19.6%)	1,624 (20.1%)	2,597 (16.3%)	2,701 (17.0%)	-0.02
Use of Loop Diuretics - United; n (%)	189 (8.8%)	195 (9.1%)	-0.01	333 (5.9%)	336 (5.9%)	0.00	967 (12.0%)	1,047 (13.0%)	1,489 (9.4%)	1,578 (9.9%)	-0.02
Use of other diuretics- United; n (%)	36 (1.7%)	37 (1.7%)	0.00	84 (1.5%)	80 (1.4%)	0.01	136 (1.7%)	166 (2.1%)	256 (1.6%)	283 (1.8%)	-0.02
Use of nitrates-United; n (%)	53 (2.5%)	53 (2.5%)	0.00	98 (1.7%)	96 (1.7%)	0.00	393 (4.9%)	401 (5.0%)	544 (3.4%)	550 (3.5%)	-0.01
Use of other hypertension drugs; n (%)	85 (3.9%)	83 (3.9%)	0.00	151 (2.7%)	159 (2.8%)	-0.01	474 (5.9%)	436 (5.4%)	710 (4.5%)	678 (4.3%)	0.01
Use of Anti-arrhythmics; n (%)	** (0.3%)	** (0.1%)	0.04	17 (0.3%)	** (0.2%)	0.02	28 (0.3%)	27 (0.3%)	#VALUE!	#VALUE!	#VALUE!
Use of COPD/asthma meds- United; n (%)	418 (19.4%)	417 (19.4%)	0.00	941 (16.6%)	1,113 (19.6%)	-0.08	1,885 (23.4%)	1,847 (22.9%)	3,244 (20.4%)	3,377 (21.2%)	-0.02
Use of statins; n (%)	707 (32.8%)	726 (33.7%)	-0.02	1,422 (25.1%)	1,416 (25.0%)	0.00	3,609 (44.7%)	3,654 (45.3%)	5,738 (36.1%)	5,796 (36.5%)	-0.01
Use of other lipid-lowering drugs; n (%)	115 (5.3%)	133 (6.2%)	-0.04	293 (5.2%)	306 (5.4%)	-0.01	606 (7.5%)	620 (7.7%)	1,014 (6.4%)	1,059 (6.7%)	-0.01
Use of antiplatelet agents; n (%)	91 (4.2%)	95 (4.4%)	-0.01	223 (3.9%)	210 (3.7%)	0.01	597 (7.4%)	586 (7.3%)	911 (5.7%)	891 (5.6%)	0.00
Use of heparin and other low-molecular weight heparins; n (%)	243 (11.3%)	207 (9.9%)	0.06	** (0.0%)	** (0.0%)	#DIV/0!	650 (8.8%)	484 (6.0%)	#VALUE!	#VALUE!	#VALUE!
Use of NSAIDs; n (%)	489 (22.7%)	440 (20.4%)	0.06	1,388 (24.5%)	1,337 (23.6%)	0.02	1,650 (20.5%)	1,599 (19.8%)	3,527 (22.2%)	3,376 (21.2%)	0.02
Use of oral corticosteroids; n (%)	619 (28.8%)	619 (28.3%)	0.00	1,372 (24.2%)	1,678 (29.6%)	-0.12	2,737 (33.9%)	2,708 (33.6%)	4,728 (29.7%)	5,005 (31.5%)	-0.04
Use of bisphosphonate (United); n (%)	58 (2.7%)	63 (2.9%)	-0.01	48 (0.8%)	72 (1.3%)	-0.05	352 (4.4%)	348 (4.3%)	458 (2.9%)	483 (3.0%)	-0.01
Use of opioids- United; n (%)	1,105 (51.3%)	1,065 (49.5%)	0.04	3,029 (53.4%)	3,012 (53.1%)	0.01	3,819 (47.4%)	3,797 (47.1%)	7953 (50.0%)	7874 (49.5%)	0.01
Use of antidepressants; n (%)	614 (28.5%)	621 (28.8%)	-0.01	1,416 (25.0%)	1,411 (24.9%)	0.00	2,513 (31.2%)	2,528 (31.3%)	4,543 (28.6%)	4,560 (28.7%)	0.00
Use of antipsychotics; n (%)	109 (5.1%)	120 (5.6%)	-0.02	211 (3.7%)	204 (3.6%)	0.01	453 (5.6%)	461 (5.7%)	773 (4.9%)	785 (4.9%)	0.00
Labs											
Lab values- HbA1c (%) v3; n (%)	259 (12.0%)	263 (12.2%)	-0.01	42 (0.7%)	49 (0.9%)	-0.02	N/A	N/A	301 (3.8%)	312 (4.0%)	-0.01
Lab values- HbA1c (%) (within 3 months) v3; n (%)	164 (7.6%)	161 (7.5%)	0.00	27 (0.5%)	41 (0.7%)	-0.03	N/A	N/A	191 (2.4%)	202 (2.6%)	-0.01
Lab values- HbA1c (%) (within 6 months) v3; n (%)	259 (12.0%)	263 (12.2%)	-0.01	42 (0.7%)	49 (0.9%)	-0.02	N/A	N/A	301 (3.8%)	312 (4.0%)	-0.01
Lab values- BNP; n (%)	23 (1.1%)	29 (1.3%)	-0.02	** (0.0%)	** (0.1%)	-0.04	N/A	N/A	#VALUE!	#VALUE!	#VALUE!
Lab values- BNP (within 3 months); n (%)	23 (1.1%)	27 (1.3%)	-0.02	** (0.0%)	** (0.1%)	-0.04	N/A	N/A	#VALUE!	#VALUE!	#VALUE!
Lab values- BNP (within 6 months); n (%)	23 (1.1%)	29 (1.3%)	-0.02	** (0.0%)	** (0.1%)	-0.04	N/A	N/A	#VALUE!	#VALUE!	#VALUE!
Lab values- BUN (mg/dl); n (%)	508 (23.6%)	589 (27.4%)	-0.09	51 (0.9%)	68 (1.2%)	-0.03	N/A	N/A	559 (7.1%)	657 (8.4%)	-0.05
Lab values- BUN (mg/dl) (within 3 months); n (%)	358 (16.6%)	415 (19.3%)	-0.07	36 (0.6%)	53 (0.9%)	-0.03	N/A	N/A	394 (5.0%)	468 (6.0%)	-0.04
Lab values- BUN (mg/dl) (within 6 months); n (%)	508 (23.6%)	589 (27.4%)	-0.09	51 (0.9%)	68 (1.2%)	-0.03	N/A	N/A	559 (7.1%)	657 (8.4%)	-0.05
Lab values- Creatinine (mg/dl) v2; n (%)	512 (23.8%)	608 (28.2%)	-0.10	52 (0.9%)	74 (1.3%)	-0.04	N/A	N/A	564 (7.2%)	682 (8.7%)	-0.06
Lab values- Creatinine (mg/dl) (within 3 months) v2; n (%)	359 (16.7%)	431 (20.0%)	-0.09	37 (0.7%)	57 (1.0%)	-0.03	N/A	N/A	396 (5.1%)	488 (6.2%)	-0.05
Lab values- Creatinine (mg/dl) (within 6 months) v2; n (%)	512 (23.8%)	608 (28.2%)	-0.10	52 (0.9%)	74 (1.3%)	-0.04	N/A	N/A	564 (7.2%)	682 (8.7%)	-0.06
Lab values- HDL level (mg/dl); n (%)	314 (14.6%)	352 (16.3%)	-0.05	35 (0.6%)	44 (0.8%)	-0.02	N/A	N/A	349 (4.5%)	396 (5.1%)	-0.03
Lab values- HDL level (mg/dl) (within 3 months); n (%)	179 (8.3%)	191 (8.9%)	-0.02	21 (0.4%)	28 (0.5%)	-0.01	N/A	N/A	200 (2.6%)	219 (2.8%)	-0.01
Lab values- HDL level (mg/dl) (within 6 months); n (%)	314 (14.6%)	352 (16.3%)	-0.05	35 (0.6%)	44 (0.8%)	-0.02	N/A	N/A	349 (4.5%)	396 (5.1%)	-0.03
Lab values- LDL level (mg/dl); n (%)	324 (15.0%)	363 (16.9%)	-0.05	38 (0.7%)	44 (0.8%)	-0.01	N/A	N/A	362 (4.6%)	407 (5.2%)	-0.03
Lab values- LDL level (mg/dl) (within 3 months); n (%)	181 (8.4%)	197 (9.2%)	-0.03	24 (0.4%)	28 (0.5%)	-0.01	N/A	N/A	205 (2.6%)	225 (2.9%)	-0.02
Lab values- LDL level (mg/dl) (within 6 months); n (%)	324 (15.0%)	363 (16.9%)	-0.05	38 (0.7%)	44 (0.8%)	-0.01	N/A	N/A	362 (4.6%)	407 (5.2%)	-0.03
Lab values- NT-proBNP; n (%)	** (0.2%)	** (0.3%)	-0.02	0 (0.0%)	0 (0.0%)	#DIV/0!	N/A	N/A	#VALUE!	#VALUE!	#VALUE!
Lab values- NT-proBNP (within 3 months); n (%)	** (0.2%)	** (0.3%)	-0.02	0 (0.0%)	0 (0.0%)	#DIV/0!	N/A	N/A	#VALUE!	#VALUE!	#VALUE!
Lab values- NT-proBNP (within 6 months); n (%)	** (0.2%)	** (0.3%)	-0.02	0 (0.0%)	0 (0.0%)	#DIV/0!	N/A	N/A	#VALUE!	#VALUE!	#VALUE!
Lab values- Total cholesterol (mg/dl) v2; n (%)	321 (14.9%)	355 (16.5%)	-0.04	35 (0.6%)	45 (0.8%)	-0.02	N/A	N/A	356 (4.5%)	400 (5.1%)	-0.03
Lab values- Total cholesterol (mg/dl) (within 3 months) v2; n (%)	183 (8.5%)	192 (8.9%)	-0.01	21 (0.4%)	29 (0.5%)	-0.01	N/A	N/A	204 (2.6%)	221 (2.8%)	-0.01
Lab values- Total cholesterol (mg/dl) (within 6 months) v2; n (%)	321 (14.9%)	355 (16.5%)	-0.04	35 (0.6%)	45 (0.8%)	-0.02	N/A	N/A	356 (4.5%)	400 (5.1%)	-0.03
Lab values- Triglyceride level (mg/dl); n (%)	316 (14.7%)	351 (16.3%)	-0.04	34 (0.6%)	43 (0.8%)	-0.02	N/A	N/A	350 (4.5%)	394 (5.0%)	-0.02

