Power	0.967396851

- MarketScan

Non-inferiority Analysis	
Number of patients matched	18,776
Reference	9,388
Exposed	9,388
Risk per 1,000 patients	14.88
Assumed HR from RCT	1.12
Alpha (2-sided)	0.05
Non-inferiority margin	2
Number of events expected	279.38688
Power	0.998048094

○ Medicare

Non-inferiority Analysis	
Number of patients matched	32,386
Reference	16,193
Exposed	16,193
Risk per 1,000 patients	13.64
Assumed HR from RCT	1.12
Alpha (2-sided)	0.05
Non-inferiority margin	2
Number of events expected	441.74504
Power	0.999982118

- Stop analyses until balance and final power assessment are reviewed by primary investigators, FDA, and assigned members of advisory board.

Reviewed by PI:		Date reviewed:	
Reviewed by FDA:		Date reviewed:	
Reasons for stopping analysis (if required):			

9. Balance Assessment

Action report links:

Optum: <https://bwh-dope.aetion.com/projects/details/1527/rwrs/67705>

Marketscan: <https://bwh-dope.aetion.com/projects/details/1653/rwrs/67706>

Medicare: <https://bwh-dope.aetion.com/projects/details/1525/rwrs/67894>

Date conducted: 3/28/2021

After review of initial feasibility and power analyses, complete creation of the remaining covariates from Section 6.2. Again, using the dummy outcome of a 90-day gap in database enrollment, complete a 1:1 PS-matched analysis. The PS should include the complete list of covariates.

- Provide plot of PS distributions stratified by treatment group.

Note- Please refer to **Appendix B**.

- Report covariate balance after matching.

Note- Please refer to **Appendix B**.

- Report reasons for censoring by treatment group.

	Overall	Referent	Exposure
Dummy outcome	0 (0.0%)	0 (0.0%)	0 (0.0%)
Death	477 (1.50%)	218 (1.37%)	259 (1.63%)
Start of an additional exposure	1,584 (4.98%)	1,023 (6.44 %)	561 (3.53%)
End of index exposure	23,632 (74.35%)	11,350 (71.42%)	12,282 (77.28%)
Specified date reached	1,617 (5.09%)	875 (5.51%)	742 (4.67%)
End of patient enrollment	2,079 (6.54%)	1,046 (6.58%)	1,033 (6.50%)
Switch to other NOACs (for censoring) + nursing home admission	2,397 (7.54%)	1,381 (8.69%)	1,016 (6.39%)

- Report follow-up time by treatment group.

Median Follow-Up Time (Days) [IQR]			
Patient Group	Optum	MarketScan	Medicare
Overall Patient Population	70 [36-174]	91 [38-184]	97 [38-195]
Referent	75 [38-173]	92 [40-178]	100 [41-199]
Exposure	65 [33-175]	91 [38-188]	88 [38-190]

10. Final Power Assessment

Date conducted: 03/28/2021

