Drug abuse or dependence; n (%)	311 (2.8%)	223 (3.5%)	-0.04	410 (1.8%)	187 (2.0%)	-0.01	276 (0.8%)	187 (1.2%)	-0.04	997 (1.5%)	597 (1.9%)	-0.03
COPD; n (%)	1,833 (16.8%)	973 (15.1%)	0.05	2,312 (10.0%)	894 (9.5%)	0.02	7,353 (22.4%)	3,421 (21.1%)	0.03	11498 (17.2%)	5288 (16.5%)	0.02
Asthma; n (%)	1,395 (12.8%)	775 (12.0%)	0.02	2,390 (10.4%)	1,048 (11.1%)	-0.02	3,700 (11.2%)	1,853 (11.4%)	-0.01	7485 (11.2%)	3676 (11.5%)	-0.01
Obstructive sleep apnea; n (%)	1,392 (12.7%)	846 (13.1%)	-0.01	2,397 (10.4%)	1,187 (12.6%)	-0.07	3,411 (10.4%)	1,712 (10.6%)	-0.01	7200 (10.8%)	3745 (11.7%)	-0.03
Pneumonia; n (%)	1,796 (16.4%)	989 (15.3%)	0.03	3,434 (14.9%)	1,343 (14.3%)	0.02	5,572 (16.9%)	2,491 (15.4%)	0.04	10802 (16.2%)	4823 (15.0%)	0.03
Other Medications												
Use of ACE inhibitors; n (%)	2,648 (24.2%)	1,294 (20.1%)	0.10	4,813 (20.9%)	1,698 (18.1%)	0.07	10,148 (30.8%)	4,664 (28.7%)	0.05	17609 (26.3%)	7656 (23.9%)	0.06
Use of ARBs; n (%)	1,386 (12.7%)	923 (14.3%)	-0.05	2,855 (12.4%)	1,146 (12.2%)	0.01	6,221 (18.9%)	3,261 (20.1%)	-0.03	10462 (15.6%)	5330 (16.6%)	-0.03
Use of Loop Diuretics - United; n (%)	917 (8.4%)	405 (6.3%)	0.08	1,580 (6.9%)	503 (5.3%)	0.07	4,381 (13.3%)	1,780 (11.0%)	0.07	6878 (10.3%)	2688 (8.4%)	0.07
Use of other diuretics- United; n (%)	140 (1.3%)	82 (1.3%)	0.00	316 (1.4%)	119 (1.3%)	0.01	625 (1.9%)	279 (1.7%)	0.02	1081 (1.6%)	480 (1.5%)	0.01
Use of nitrates-United; n (%)	291 (2.7%)	128 (2.0%)	0.05	471 (2.0%)	141 (1.5%)	0.04	1,680 (5.1%)	709 (4.4%)	0.03	2442 (3.7%)	978 (3.0%)	0.04
Use of other hypertension drugs; n (%)	467 (4.3%)	203 (3.1%)	0.06	755 (3.3%)	242 (2.6%)	0.04	1,947 (5.9%)	854 (5.3%)	0.03	3169 (4.7%)	1299 (4.0%)	0.03
Use of Anti-arrhythmics; n (%)	24 (0.2%)	13 (0.2%)	0.00	70 (0.3%)	19 (0.2%)	0.02	118 (0.4%)	49 (0.3%)	0.02	212 (0.3%)	81 (0.3%)	0.00
Use of COPD/asthma meds- United; n (%)	1,985 (18.2%)	1,117 (17.3%)	0.02	4,137 (18.0%)	1,708 (18.2%)	-0.01	7,383 (22.4%)	3,707 (22.9%)	-0.01	13505 (20.2%)	6532 (20.4%)	0.00
Use of statins; n (%)	3,339 (30.5%)	1,881 (29.2%)	0.03	5,891 (25.6%)	2,195 (23.3%)	0.05	14,704 (44.7%)	7,286 (44.9%)	0.00	23934 (35.8%)	11362 (35.4%)	0.01
Use of other lipid-lowering drugs; n (%)	650 (5.9%)	305 (4.7%)	0.05	1,443 (6.3%)	464 (4.9%)	0.06	2,506 (7.6%)	1,182 (7.3%)	0.01	4599 (6.9%)	1951 (6.1%)	0.03
Use of antiplatelet agents; n (%)	402 (3.7%)	251 (3.9%)	-0.01	974 (4.2%)	341 (3.6%)	0.03	2,429 (7.4%)	1,076 (6.6%)	0.03	3805 (5.7%)	1668 (5.2%)	0.02

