Use of heparin and other low-molecular weight heparins; n (%)	5,843 (53.4%)	209 (3.3%)	1.34	19 (0.1%)	** (0.0%)	0.04	15,058 (45.8%)	487 (3.0%)	1.15	20920 (31.3%)	#VALUE!	#VALUE!
Use of NSAIDs; n (%)	2,235 (20.4%)	1,367 (21.2%)	-0.02	4,992 (21.7%)	2,348 (25.0%)	-0.08	6,301 (19.2%)	3,269 (20.2%)	-0.03	13528 (20.2%)	6984 (21.8%)	-0.04
Use of oral corticosteroids; n (%)	2,937 (26.9%)	1,838 (28.5%)	-0.04	6,039 (26.2%)	2,595 (27.6%)	-0.03	10,634 (32.3%)	5,310 (32.7%)	-0.01	19610 (29.3%)	9743 (30.4%)	-0.02
Use of bisphosphonate (United); n (%)	377 (3.4%)	131 (2.0%)	0.09	396 (1.7%)	101 (1.1%)	0.05	1,572 (4.8%)	625 (3.9%)	0.04	2345 (3.5%)	857 (2.7%)	0.05
Use of opioids- United; n (%)	5,636 (51.5%)	3,020 (46.8%)	0.09	12,644 (54.9%)	4,824 (51.3%)	0.07	15,530 (47.2%)	7,363 (45.4%)	0.04	33810 (50.6%)	15207 (47.4%)	0.06
Use of antidepressants; n (%)	2,945 (26.9%)	1,722 (26.7%)	0.00	5,760 (25.0%)	2,242 (23.8%)	0.03	9,959 (30.3%)	4,877 (30.1%)	0.00	18664 (27.9%)	8841 (27.6%)	0.01
Use of antipsychotics; n (%)	480 (4.4%)	309 (4.8%)	-0.02	807 (3.5%)	331 (3.5%)	0.00	1,719 (5.2%)	842 (5.2%)	0.00	3006 (4.5%)	1482 (4.6%)	0.00
Labs												
Lab values- HbA1c (%); v3; n (%)	881 (8.1%)	779 (12.1%)	-0.13	205 (0.9%)	83 (0.9%)	0.00	N/A	N/A	#VALUE!	1,086 (3.2%)	862 (5.4%)	-0.11
Lab values- HbA1c (%)(within 3 months); v3; n (%)	565 (5.2%)	499 (7.7%)	-0.10	150 (0.7%)	64 (0.7%)	0.00	N/A	N/A	#VALUE!	715 (2.1%)	563 (3.6%)	-0.09
Lab values- HbA1c (%)(within 6 months); v3; n (%)	881 (8.1%)	779 (12.1%)	-0.13	205 (0.9%)	83 (0.9%)	0.00	N/A	N/A	#VALUE!	1,086 (3.2%)	862 (5.4%)	-0.11
Lab values- BNP; n (%)	96 (0.9%)	85 (1.3%)	-0.04	** (0.0%)	** (0.1%)	-0.04	N/A	N/A	#VALUE!	#VALUE!	#VALUE!	#VALUE!
Lab values- BNP (within 3 months); n (%)	89 (0.8%)	79 (1.2%)	-0.04	** (0.0%)	** (0.0%)	#DIV/0!	N/A	N/A	#VALUE!	#VALUE!	#VALUE!	#VALUE!
Lab values- BNP (within 6 months); n (%)	96 (0.9%)	85 (1.3%)	-0.04	** (0.0%)	** (0.1%)	-0.04	N/A	N/A	#VALUE!	#VALUE!	#VALUE!	#VALUE!
Lab values- BUN (mg/dl); n (%)	2,195 (20.1%)	1,688 (26.2%)	-0.15	208 (0.9%)	118 (1.3%)	-0.04	N/A	N/A	#VALUE!	2,403 (7.1%)	1,806 (11.4%)	-0.15
Lab values- BUN (mg/dl) (within 3 months); n (%)	1,542 (14.1%)	1,182 (18.3%)	-0.11	153 (0.7%)	85 (0.9%)	-0.02	N/A	N/A	#VALUE!	1,695 (5.0%)	1,267 (8.0%)	-0.12
Lab values- BUN (mg/dl) (within 6 months); n (%)	2,195 (20.1%)	1,688 (26.2%)	-0.15	208 (0.9%)	118 (1.3%)	-0.04	N/A	N/A	#VALUE!	2,403 (7.1%)	1,806 (11.4%)	-0.15

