Appendix B

Lab values-Triglyceride level (mg/dl) (within 3 months); n (%)	753 (6.9%)	590 (9.2%)	-0.08	110 (0.5%)	49 (0.5%)	0.00	N/A	N/A	#VALUE!	863 (2.5%)	639 (4.0%)	-0.08
Lab values-Triglyceride level (mg/dl) (within 6 months); n (%)	1,335 (12.2%)	1,038 (16.1%)	-0.11	177 (0.8%)	80 (0.9%)	-0.01	N/A	N/A	#VALUE!	1,512 (4.5%)	1,118 (7.1%)	-0.11
Lab result number- HbA1c (%) mean (only 2 to 20 included)v4	876	776		164	80		N/A	N/A		1,040	856	
...mean (sd)	6.67 (1.48)	6.52 (1.50)	0.10	7.09 (1.41)	7.06 (1.75)	0.02	N/A	N/A	#VALUE!	6.74 (1.47)	6.57 (1.53)	0.11
...Missing; n (%)	10,060 (92.0%)	5,672 (88.0%)	0.13	22,876 (99.3%)	9,325 (99.1%)	0.02	N/A	N/A	#VALUE!	32,936 (96.9%)	14,997 (94.6%)	0.11
Lab result number- BNP mean v2	96	85		8	6		N/A	N/A		104	91	
...mean (sd)	83.18 (129.35)	114.60 (175.32)	-0.20	70.15 (59.71)	47.52 (53.77)	0.40	N/A	N/A	#VALUE!	82.18 (126.43)	110.18 (171.77)	-0.19
...Missing; n (%)	10,840 (99.1%)	6,363 (98.7%)	0.04	23,032 (100.0%)	9,399 (99.9%)	0.04	N/A	N/A	#VALUE!	33,872 (99.7%)	15,762 (99.4%)	0.04
Lab result number- BUN (mg/dl) mean v2	2,195	1,688		208	118		N/A	N/A		2,403	1,806	
...mean (sd)	17.31 (6.76)	16.03 (5.52)	0.21	1,651.89 (16,887.31)	1,033.14 (11,045.39)	0.04	N/A	N/A	#VALUE!	158.80 (4959.53)	82.49 (2813.69)	0.02
...Missing; n (%)	8,741 (79.9%)	4,760 (73.8%)	0.15	22,832 (99.1%)	9,287 (98.7%)	0.04	N/A	N/A	#VALUE!	31,573 (92.9%)	14,047 (88.6%)	0.15
Lab result number- Creatinine (mg/dl) mean (only 0.1 to 15 included)v3	2,195	1,735		206	129		N/A	N/A		2,401	1,864	
...mean (sd)	0.97 (0.30)	0.94 (0.23)	0.11	1.00 (0.33)	0.95 (0.24)	0.17	N/A	N/A	#VALUE!	0.97 (0.30)	0.94 (0.23)	0.11
...Missing; n (%)	8,741 (79.9%)	4,713 (73.1%)	0.16	22,834 (99.1%)	9,276 (98.6%)	0.05	N/A	N/A	#VALUE!	31,575 (92.9%)	13,989 (88.2%)	0.16
Lab result number- HDL level (mg/dl) mean (only <=5000 included)v2	1,327	1,026		185	80		N/A	N/A		1,512	1,106	
...mean (sd)	53.56 (16.61)	52.84 (16.18)	0.04	47.72 (21.06)	49.04 (15.24)	-0.07	N/A	N/A	#VALUE!	52.85 (17.22)	52.57 (16.42)	0.02
...Missing; n (%)	9,609 (87.9%)	5,422 (84.1%)	0.11	22,855 (99.2%)	9,325 (99.1%)	0.01	N/A	N/A	#VALUE!	32,464 (95.5%)	14,747 (93.0%)	0.11
Lab result number- LDL level (mg/dl) mean (only <=5000 included)v2	1,353	1,033		176	76		N/A	N/A		1,529	1,109	
...mean (sd)	102.31 (36.16)	106.34 (37.86)	-0.11	94.29 (41.51)	103.08 (42.40)	-0.21	N/A	N/A	#VALUE!	101.39 (36.82)	106.12 (38.20)	-0.13

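### In the MarketScan match, oral corticosteroid use is printed as worse balanced after matching (std. diff. -0.12) than before (-0.03); propensity score membership and source counts should be confirmed before outcomes are analysed

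*Combined protocol and SAP*

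**What the plan says.** Section 9 (Balance Assessment) calls for a 1:1 match on the dummy outcome after the remaining covariates have been built, and states: "The PS should include the complete list of covariates". It asks for covariate balance after matching and refers to Appendix B.

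The MarketScan entries in Appendix B, warfarin first, are:

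- "Use of oral corticosteroids; n": before matching "6,039 (26.2%) 2,595 (27.6%) -0.03"; after matching "1,372 (24.2%) 1,678 (29.6%) -0.12".
- "Use of COPD/asthma meds- United; n": before matching "4,137 (18.0%) 1,708 (18.2%) -0.01"; after matching "941 (16.6%) 1,113 (19.6%) -0.08".

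Sections 8 and 10 halt the work until the investigators, FDA and advisory board members have reviewed balance and final power. The text gives no numerical balance criterion, no action for a row that fails, and no comment on these two rows. The review fields and section 13 (Comparative Analyses) are blank.

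**The concern.** A covariate that starts almost balanced and is in a working propensity score should stay close to balance. Here the MarketScan arms move apart: warfarin falls below both unmatched arms and rivaroxaban rises above both. That is hard to reconcile with the rule in section 9.

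Oral corticosteroid use plausibly marks illness that raises the risk of both VTE and bleeding. If the imbalance is real, the MarketScan hazard ratio would lean against rivaroxaban, and the confidence interval would not reflect it. MarketScan supplies more than a third of the expected events. The pooled column shows only -0.04 for corticosteroids, so a reader of the pooled balance would miss the row.

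**Working it through.** **Denominators.** Before matching, from the HbA1c rows of Appendix B (missing, "22,876 (99.3%) 9,325 (99.1"%), plus observed): 22,876 + 164 = 23,040 warfarin and 9,325 + 80 = 9,405 rivaroxaban. These sum to 32,445, the final cohort in section 5.3. After matching: 5,675 per arm (section 10).

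**Column order.** Before matching, all 9,405 MarketScan rivaroxaban patients had a hospitalization, against 23,039 of 23,040 on warfarin. After matching, the first column shows 5,674 of 5,675, so it must be warfarin. Rivaroxaban carries the corticosteroid excess.

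**Reproducing the printed values.** d = (p_W - p_R) / sqrt{[p_W(1 - p_W) + p_R(1 - p_R)] / 2}.

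- Corticosteroids before: 6,039/23,040 = 0.2621 and 2,595/9,405 = 0.2759; d = -0.031 (printed -0.03).
- Corticosteroids after: 1,372/5,675 = 0.2418 and 1,678/5,675 = 0.2957; d = -0.0539/0.4425 = -0.122 (printed -0.12).
- COPD/asthma drugs before: 0.1796 and 0.1816; d = -0.005 (printed -0.01).
- COPD/asthma drugs after: 941/5,675 = 0.1658 and 1,113/5,675 = 0.1961; d = -0.079 (printed -0.08).

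**Could it be chance?** The standard error of d is about sqrt(2/5,675) = 0.019. A pooled two-proportion z, used only as a yardstick, gives -0.0539/0.00832 = -6.5 for corticosteroids (306 more users on rivaroxaban) and -4.2 for COPD/asthma drugs (172 more).

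**Comparison rows after matching.**

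| Row | Database | Warfarin | Rivaroxaban |
|---|---|---|---|
| Oral corticosteroids | Optum | 619 | 619 |
| Oral corticosteroids | Medicare | 33.9% | 33.6% |
| COPD/asthma drugs | Optum | 418 | 417 |
| COPD/asthma drugs | Medicare | 23.4% | 22.9% |
| COPD diagnosis | MarketScan | 10.3% | 10.0% |
| Asthma diagnosis | MarketScan | 11.1% | 11.1% |

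Statins, opioids and antidepressants in MarketScan are also within 0.01.

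**Pooled.** 619 + 1,372 + 2,737 = 4,728 and 619 + 1,678 + 2,708 = 5,005, which are the printed totals. The section 9 censoring counts (excluding the dummy outcome, which is zero) sum to 15,893 per arm. On that denominator d = -0.038.

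**Size if real.** Assume that corticosteroid use multiplies VTE risk by RR, given the balanced covariates. The documents give no value for RR. The MarketScan hazard ratio is then multiplied by [1 + 0.2957(RR - 1)] / [1 + 0.2418(RR - 1)]:

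- RR = 1.5: 1.1479/1.1209 = 1.024
- RR = 2: 1.2957/1.2418 = 1.043
- RR = 3: 1.5914/1.4836 = 1.073

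The MarketScan share of expected events is 168.888/457.68 = 0.37 on the printed section 10 totals. Section 10 prints 8,671 Medicare patients per arm, but the section 9 censoring counts imply 15,893 - 2,153 - 5,675 = 8,065. With 8,065 and the section 8 Medicare risk of 13.64 per 1,000, the share is 168.9/446.5 = 0.38. Applying either share on the log scale, the pooled hazard ratio rises by about 0.9%, 1.6% and 2.6% to 2.7%. A true 1.12 would appear as about 1.13 to 1.15.

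**The case against.** Four stronger readings are tempting, and the documents support none of them.

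- **That the MarketScan propensity score is shown to be at fault and the hazard ratio biased.** The model is not visible. A table error would leave no imbalance at all, and other printed cells after matching do not agree with their counts: Optum corticosteroids show 619 as both 28.8% and 28.3% on equal arms, and the pooled flu vaccine count is 3,040 where the databases sum to 329 + 576 + 2,499 = 3,404. The corticosteroid counts, percentages, std. diff. and pooled sum do agree with one another, so an error there is neither shown nor excluded.
- **That nothing in the plan would catch the row.** Sections 8 and 10 stop the work for exactly this review, and section 8 expects the protocol to be refined after feedback. What is missing is narrower: a threshold and a remedy.
- **That a whole group of drug rows fails.** Only corticosteroids exceed the customary 0.10, which is itself an outside convention. COPD/asthma drugs worsen but stay below it. CNS stimulants reach only -0.042 (65 vs 93 patients). Bisphosphonates change sign (+0.055 to -0.041), but their absolute imbalance shrinks.
- **That the non-inferiority conclusion is at risk.** The shift is small, and an excess of higher-risk patients on rivaroxaban cannot create false non-inferiority. The risk ratios are assumptions, and balance on related diagnoses may limit the effect further.

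What stands is the anomaly: a divergence confined to one database, too large for chance, in a variable that section 9 says should be in the score.

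**Conclusion.** The concern holds as an unexplained imbalance that should be resolved before outcomes are analysed. The printed figures reproduce and the direction is settled. The cause (omission, a different definition, or wrong counts) is not shown, so bias is conditional on the imbalance being real. In that case the MarketScan hazard ratio would be inflated by about 2% to 7% and the pooled one by about 1% to 3%, under assumed risk ratios of 1.5 to 3. This would not overturn the margin of 2.0. It matters for agreement with the trial's 1.12, and because an omitted variable in one database could signal a wider specification error. It merits correction but is not a fatal fault.

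**What to change.** At the planned balance review, before section 13 is run:

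1. Confirm for MarketScan that oral corticosteroids and COPD/asthma drugs are in the propensity score, with the same definitions as in Appendix B, and check the source counts.
2. If a variable was omitted or misdefined, correct the score, re-match on the dummy outcome, and re-issue the balance and final power tables. If the table is wrong, correct it.
3. State a balance criterion in section 9, applied within each database as well as pooled. If a covariate measured in all patients still exceeds 0.10 (a convention, not taken from the documents), adjust for it in the MarketScan outcome model. Exclude lab means from this trigger: they are observed in about 1% of matched MarketScan patients, and values such as BNP at -0.75 rest on 2 vs 3 patients.

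The cost is at most one propensity score run in one database, without sight of outcomes. Matched N may change slightly; printed MarketScan power is 0.965, so a small loss is affordable.
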